### 7.8.2 Pharmacokinetic considerations

Progression of dose levels (entrance of a new cohort at the next higher dose level) will also depend on review of the naltrexone PK data of the prior dose level. AUC (0-T) will be calculated for T=4 weeks, T= 8 weeks, and T=12 weeks for each subject, statistically summarized for the group, and the mean values will be compared to the reference values for the most sensitive animal species (dog) for which AUC was 3,267 ng/ml x hr up to 4 weeks, 6,117 ng/ml x hr up to

8 weeks, and 13.239 ng/ml x hr up to 12 weeks. In addition, the mean Cmax for dog for which the reference value was 42 ng/ml. If the mean clinical Biopin AUC or Cmax values exceed any of these reference values by 31%, the new cohort will not be entered until further consultation with the FDA.

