Pharmacokinetics (naltrexone and its major metabolite, 6-beta-naltrexol)				
Blood sampling (29 samples)			Predose. Hours 1, 3, 6, 12, 24, 48 and 72. Days 7 and 10. Weeks 2, 3, 4, 5, 6, 7, 8, 9, 10, 11	Week 12: pre-explant and 1, 3, 6, 12, 24 hrs after explant (as resident). 48,72, and 96 hrs (non resident).

 Heart rate (sitting), blood pressure (sitting), respiratory rate, oral temperature

 ALT, albumin, alkaline phosphatase, AST, bilirubin (total and direct), calcium, chloride, cholesterol, creatinine, GGT, glucose, phosphate, potassium, sodium, total protein, uric acid, and blood urea nitrogen (BUN).

 Hemoglobin, hematocrit, red blood cell count (RBC), reticulocytes, white blood cell count (WBC), platelets

 Fibrinogen, prothrombin time (PT), and partial thromboplastin time (PTT).

 Subjects return for a non-residential visit on week 14 for surgical evaluation of explantation site

 For non-resident days, window will be target day [Week 2 (Day 14), Week 3 (Day 21), etc.] +/- 3 days

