BIOPIN 6 contains naltrexone, and the excipients poly-D,L Lactic Acid and polycaprolactone for subcutaneous implantation. Via this formulation and its site of administration, it is intended that BIOPIN 6 can be given every 6 months, which should aid patient compliance thus anti-opioid efficacy. In addition, the BIOPIN 6 clinical development plan will examine BIOPIN 6 doses that lead to drug levels in excess of those resulting from Vivitrol administration. If these BIOPIN 6 doses are well-tolerated, the higher blood levels of naltrexone should also lead to greater anti-opioid efficacy.

The present protocol constitutes the first administration of BIOPIN 6 to humans. The primary endpoints are pharmacokinetics and safety of lower, mid, and higher BIOPIN 6 doses.

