**Figure 1: Subjects Sustaining Varying Percentages of Opioid-Free Weeks**

[figure not shown]
A greater percentage of subjects in the Vivitrol group remained in the study compared to the placebo group.

Pharmacokinetics: The PK of naltrexone resulting from Vivitrol administration is shown below [2]

**Figure 2: Mean plasma concentration of naltrexone (top) and 6b-naltrexol (bottom) following single dose administration of long-acting naltrexone 190 (open**

boxes) and 380 (closed circles) mg. Left panel: Days 0 to 56; right panel: Days 0 to 5 [2]

In this study, after naltrexone 380 mg IM, peak naltrexone levels of 10 ng/ml were achieved at day 2 and fell to 2 ng/ml on day 28. Peak 6b-naltrexole levels of 11 ng/ml on day 3 declined to 7 ng/ml on day 28.

**Adverse events:** The adverse events attributed to naltrexone (Vivitrol) administration for opioid dependence are: opioid withdrawal syndrome if administered to opioid-using persons, hepatic enzyme abnormalities, injection site pain, nasopharyngitis, insomnia, and toothache. Additional adverse events seen in the treatment of alcohol dependences are: nausea, vomiting, injection site reactions (including induration, pruritus, nodules and swelling), muscle cramps, dizziness or syncope, somnolence or sedation, anorexia, decreased appetite or other appetite disorders. Suicidality has also been reported. Platelets may modestly fall; creatine phosphokinase may modestly rise. [10]

The adverse events consequent to a competitive implant containing naltrexone were: infection, irritation, side-effects of naltrexone (nausea and vomiting, weight loss or change in mood; six cases) or a requirement for opioid analgesia for co-morbid conditions (one acute trauma and one chronic rheumatological condition). [11]

The two excipients in BIOPIN 6 are polylactide and polycaprolactone, both of which are widely used clinically. Polylactide PLA has shown promise in a plethora of healthcare applications such

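### The 12-week dog reference AUC in Protocol 7.8.2 (13.239 ng/ml x hr) is impossible beside the 4- and 8-week values of 3,267 and 6,117

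*Protocol*

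**What the plan says.** Protocol 7.8.2 makes dose progression depend on naltrexone PK as well as safety. The compared quantity is defined first: "AUC (0-T) will be calculated for T=4 weeks, T= 8 weeks, and T=12 weeks for each subject". Group means are then set against values for the dog, taken as the most sensitive species. The first two of these references appear as "for which AUC was 3,267 ng/ml x hr up to 4 weeks, 6,117 ng/ml x hr up to" the 8-week point. The third, which is the one at issue here, closes the series: "8 weeks, and 13.239 ng/ml x hr up to 12 weeks". A peak concentration is added, "for which the reference value was 42 ng/ml". The consequence is explicit: if the clinical means "exceed any of these reference values by 31%, the new cohort will not be entered until further consultation with the FDA".

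The rule therefore has four limits: three cumulative AUCs in one unit, and Cmax. Neither document gives the 12-week dog value anywhere else. Protocol 5.3 summarises the progression rule without numbers, and Protocol 4.3 (nonclinical data) is redacted.

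**The concern.** All three AUC references start at time 0. Concentrations are never negative, so a cumulative AUC can only stay level or rise as the interval lengthens. A 12-week value of 13.239 after 6,117 at 8 weeks cannot be right in the same unit.

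The figure is an operative limit in the rule that decides whether people may receive the next higher dose without further regulatory consultation. Taken as it stands, it would stop essentially every active cohort once the 12-week AUC was compared. Taken as a slip, the real limit is nowhere stated, and whoever applies the rule or writes it up has to guess it.

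**Working it through.** **Inputs** (Protocol 7.8.2 unless noted)

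- Dog AUC: 3,267 to 4 weeks, 6,117 to 8 weeks, 13.239 to 12 weeks, all in ng/ml x hr
- Dog Cmax: 42 ng/ml
- Hold if a reference is exceeded by 31%, so limit = 1.31 × reference
- 4 weeks = 672 h; 12 weeks = 2,016 h

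The 12-week figure cannot be rebuilt from source because the dog data are redacted. What can be checked is whether it is consistent with its neighbours.

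**Step 1: can the series be cumulative?** The implied exposure between weeks 8 and 12 is 13.239 − 6,117 = −6,104 ng/ml x hr, which is impossible. The ratio 6,117 / 13.239 = 462.

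**Step 2: the limits.**

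| Reference | Value | × 1.31 |
|---|---|---|
| AUC to 4 weeks | 3,267 | 4,280 |
| AUC to 8 weeks | 6,117 | 8,013 |
| AUC to 12 weeks, literal | 13.239 | 17.3 |
| AUC to 12 weeks, if 13,239 | 13,239 | 17,343 |
| Cmax (ng/mL) | 42 | 55.0 |

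The 12-week limit cannot be below the 8-week limit. The literal one is 17.343 / 8,013.3 = 0.22% of that minimum.

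**Step 3: what the limit means as a concentration.** Averaged over 12 weeks, 17.343 / 2,016 = 0.0086 ng/mL, against 17,343 / 2,016 = 8.6 ng/mL. For scale, Protocol 4.4 reports that naltrexone after the 380 mg injection "fell to 2 ng/ml on day 28", and Protocol 4.1 says the programme will study "doses that lead to drug levels in excess of those resulting from Vivitrol administration". Assume, for illustration only, a 12-week mean of 2 ng/mL. Then AUC to 12 weeks = 2 × 2,016 = 4,032, which is 232 times the literal limit, 50% of the smallest possible limit (8,013) and 23% of 17,343.

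**Step 4: what the true value could be.** Assume that the AUC and Cmax references come from the same animals.

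- Floor: 6,117.
- Ceiling: exposure in weeks 8 to 12 cannot exceed Cmax held for 672 h, so 6,117 + 42 × 672 = 6,117 + 28,224 = 34,341.
- The corresponding limits are 8,013 and 44,987.

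13,239 lies inside this range and 13.239 does not.

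**Step 5: is 13,239 plausible?** Mean dog concentration by interval:

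- Weeks 0–4: 3,267 / 672 = 4.9 ng/mL
- Weeks 4–8: (6,117 − 3,267) / 672 = 4.2 ng/mL
- Weeks 8–12, if 13,239: (13,239 − 6,117) / 672 = 10.6 ng/mL

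A late rise of 10.60 / 4.24 = 2.5-fold is possible and stays below Cmax. It is large enough that the number should be looked up, not simply re-punctuated.

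**The case against.** The strongest reply is that this is a plain punctuation slip, a period for a comma. Two comma-separated values precede it, any pharmacokineticist would read 13,239, and a limit of 17.3 would be recognised as absurd. The error is in the cautious direction. SAP section 3 records that escalation ended after the second dose level because target exposure had been reached. Nothing in the documents shows that 13.239 was ever applied, or that the 12-week comparison was made before the step from 4.8 g to 9.6 g. Protocol 5.3 also ties progression to the values seen in the animal studies (plus 1 SD), so the digits in 7.8.2 are not the only statement of the rule.

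Most of this stands, and it is why the point is minor. It does not remove the error: 5.3 supplies no number, and 13,239 cannot be confirmed from what is public.

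Two caveats also stand. The text was extracted from a PDF, so a misread comma cannot be fully excluded. It is unlikely, since the other two AUC values kept theirs, and the original page will settle it. The floor of 6,117 assumes the three AUC references describe the same animals. Different animals could move it somewhat but would not plausibly explain a 462-fold shortfall.

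**Conclusion.** The concern holds, as a minor point. The 12-week dog reference is wrong as written: it lies 462-fold below a value it cannot be less than, and it turns a limit of at least 8,013 ng/ml x hr into 17.3. The 4-week, 8-week and Cmax references are not in question. The intended value is probably 13,239 (limit 17,343), but that is an inference. The protocol's own figures only place the reference between 6,117 and 34,341, on the same-animals assumption.

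No harm to subjects follows, and no further dosing decision depends on the figure. What remains is the record: the step from 4.8 g to 9.6 g took place under this rule, and the study report should describe the rule with a correct 12-week limit.

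**What to change.** Check the 12-week AUC against the dog toxicokinetic report. Correct it in Protocol 7.8.2, or issue a dated clarification, and carry the correct value and its 1.31 multiple into the study report.

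Optionally, add a row to SAP Table 11 for AUC from 0 to 12 weeks (to the pre-explant sample), which is the quantity the rule compares. The table has 4-week, 8-week and to-last rows but no 12-week one. Without it, the to-last AUC is only an approximate upper bound, because sampling continues after explant at "48,72, and 96 hrs (non resident"), up to 96 / 2,016 = 4.8% more time. The mean naltrexone concentrations in SAP Table 9 would allow an approximation.

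The cost is one number verified and, if wanted, one table row. No new data are needed, because the pre-explant Week 12 sample is already scheduled.

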### **7.9 Termination of the Study**

If, in the opinion of the investigator, the clinical observations in the study suggest that it may be unwise to continue, the investigator may terminate the study after consultation with the Study sponsor. A written statement fully documenting the reasons for such a termination will be provided to the sponsor. In addition, the sponsor may terminate the study at any time. Furthermore, if it becomes apparent that subject enrollment is unsatisfactory with respect to quality or quantity or that data recording is inaccurate or incomplete on a chronic basis, the sponsor has the right to terminate the study and remove all study materials from the investigational site. A written statement will be provided to the investigator, the IRB/IEC, and regulatory authorities, if required. In the event any serious adverse events (SAEs) are part of the reason for early termination of the study, all documentation relating to the event(s) reported to FDA must be obtained and filed appropriately.

## 8. Procedures

### 8.1 Screening: days -28 to -2

**Demographics:** Demographics data include the subject's age, gender, and race/ethnicity.

**Medical history:** A medical history will be taken during screening for all potential study subjects to assure medical fitness. Drug allergies will be queried. Drinking and smoking habits will be queried

**Physical examination:** A physical examination of the oral cavity, head, eyes, ears, nose, and throat, cardiovascular system, lungs, abdomen, extremities, skin, neuropsychiatric mental status and sensory/motor status, musculoskeletal system and general appearance will be performed during screening. Weight (kg) and height (centimeters) will be collected.

**EKG:** A 12-lead resting EKG will be obtained.

**Vital signs:** Vital signs to be assessed include sitting blood pressure and pulse rate (after sitting for at least 3 minutes). Site is allowed to repeat Screening vital signs up to 3 times towards inclusion in the trial.

**Clinical pathology:** Clinical laboratory tests will be performed at the clinical site's local clinical laboratory. The laboratories performing these assessments should be directly regulated by the College of American Pathologists (CAP) or Clinical Laboratory Improvement Act (CLIA) guidelines. The laboratory will need to provide a copy of current certification. The following tests will be performed to determine the medical fitness of the subject for participation:

**Clinical Chemistry:** ALT, Albumin, alkaline phosphatase, AST, bilirubin (total and direct), calcium, chloride, cholesterol, creatinine, GGT, glucose, phosphate, potassium, sodium, total protein, BUN, uric acid.

**Hematology:** Hemoglobin, hematocrit, red blood cell count (RBC), reticulocytes, white blood cell count (WBC), platelets.

**Coagulation:** Fibrinogen, prothrombin time (PT), partial thromboplastin time (PTT).

**Infectious Diseases:** Hepatitis B surface antigen, Hepatitis C antibody, Human immunodeficiency (HIV-1 and HIV-2) antibodies and p24 antigen, Covid antigen.

**Pregnancy tests:** A serum test for  $\beta$ -hCG will be performed. Serum HCG test at screening; urine HCG test at day (-1). For postmenopausal females, a follicle stimulating hormone test will be performed during screening.

**Urine drug tests:** Urine drug tests will be used to assess candidates for recent use of amphetamines, barbiturates, benzodiazepines, cocaine, opiates, cannabinoids, phencyclidine, propoxyphene, and methadone.

**Alcohol breathalyzer test:** An alcohol breathalyzer test measures the amount of alcohol in the blood. The subject must have a blood alcohol levels of  $\leq 0.05\%$  to be enrolled in this study.

**Naloxone challenge test:** The naloxone challenge test is performed to assess physical dependence. 0.1 mg of naloxone is administered subcutaneously. A positive test is indicative of physical dependence and consists of typical withdrawal symptoms and signs. These symptoms and signs usually last for 30-60 minutes. The test will be administered as per SOP ([Appendix C](#)).

Suicidality: Suicidality will be measured by Columbia Suicide Severity Rating Scale. Data will be collected for both “Lifetime” as well as “Past 1 month”.

Depression: Depression will be measured by the HAM-D17.

Inclusion/exclusion criteria: Verified.

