## 2.2 Protocol Timetable

Study Phase	Screening (days -28 to -2)	Day -1	Day 1 to Week 11 	Week 12 (and week 14) 
Informed consent	X			
Demographic data 	X			
Medical history	X	X (update if needed)		
Physical exam 	X	X (update if needed)	Week 4 and 8	X
Weight/height	X			
Urine drugs of abuse screen 	X	X	Week 4 and 8	X
Alcohol breath test	X			
Naloxone challenge test	X	X		
Concomitant medications	X	X	Weekly	X
Serology 	X			
Birth Control Methods/Pregnancy Test 	X	X		
C-SSRS for suicidality	X	X	Weeks 4 and 8	X
HAM-D for depression	X	X	Weeks 2,4,6,8,10	X
Inclusion/exclusion criteria	X	X		
Randomization 		X		
Residential visits		Check in on day (-1)	Check out on Day 4 (72 hours postdose)	Week 12
Non-residential visits	X		Days 7 and 10, and Weeks 2, 3, 4, 5, 6, 7, 8, 9, 10, 11	Week 12 (week 14)
Study drug (Biopin or placebo) administration by implantation			Day 1 (0 h): Insert BIOPIN implant	Remove BIOPIN implant (and week 14) 
Implant Tissue Assessment			At each residential and non-residential visit	Gross and microscopic descriptions and photos of each tissue capsule.

 Age, gender, and race/ethnicity

 Abbreviated (see Protocol Section 8)

 Amphetamines, barbiturates, benzodiazepines, cocaine, opiates, cannabinoids, phencyclidine, propoxyphene, methadone.

 Hepatitis B surface antigen, hepatitis C antibody, human immunodeficiency (HIV-1 and HIV-2) antibodies and p24 antigen, covid antigen

 Serum HCG test at screening; urine HCG test at day (-1). For postmenopausal females, a follicle stimulating hormone test will be performed during screening.

 Each dose cohort of 8 subjects randomized 6 active vs 2 placebo

Study Phase	Screening (days -28 to -2)	Day -1	Day 1 to Week 11 	Week 12 (and week 14) 
Safety and tolerability:				
Adverse event recording	X		Predose, 8, 24, 48 and 72 hours postdose. Then weekly	X
Vital signs 	X		Predose, 8, 24, 48 and 72 hours postdose. Days 7 and 10. Weeks 2, 3, 4, 5, 6, 7, 8, 9, 10, 11	X (pre and post explant)
12-lead ECG	X	X	Week 4 and 8	X (pre and post explant)
Clinical chemistries 	X		72 hours post dose; then weeks 4 and 8	X
Hematology 	X		72 hours post dose; then weeks 4 and 8	X
Coagulation 	X			

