#### **7.4 Exclusion criteria**

Subjects must have none of the exclusion criteria to be included in the study.

1. Clinically significant abnormal finding on the physical exam, medical history, electrocardiogram (EKG), or clinical laboratory results at screening. In particular, values of liver function tests (ALT, AST, bilirubin, albumin, GGT) and kidney function tests (creatinine, blood urea nitrogen) and reticulocytes shall not deviate by more than 25% from the ranges of normal.
2. Blood pressure: systolic >150 mmHg, diastolic >90 mmHg. [Europe Soc Hypertension guidelines]. Repeat measurements up to three times are acceptable.
3. Heart rate: >100 beats/minute.
4. Hemoglobin for female <11.5 and for male <12.5 are excluded.
5. Have a known or suspected history or family history of adverse reactions or hypersensitivity to the study drugs or to drugs with a similar chemical structure.
6. History or presence of gastrointestinal, hepatic or renal disease, or other condition known to interfere with the absorption, distribution, metabolism or excretion of drugs.
7. Is on anticoagulant medications other than aspirin or NSAIDs. Agree to stop aspirin or NSAIDs 1 week prior to Biopin 6 implantation
8. Used any over-the-counter (OTC) medication, nutritional or dietary supplements, herbal preparations, or vitamins within 7 days prior to the first dose of medication.
9. Used any prescription medication (except contraceptive medications and those required for use during the surgical procedure) within 14 days prior to the first dose of study medication.
10. More than moderate drinking averaged over the last month as assessed by history:
  - Moderate drinking is here defined as up to 3 drinks per week. The standard drink will be defined by the guidelines of the National Institute on Alcohol Abuse and Alcoholism (NIAAA) and will contain no more than 14 g of alcohol.
11. Smoking: Use of tobacco or nicotine-containing products within the 3-month period preceding study drug administration is exclusionary.
12. Positive urine drug screen for amphetamines, barbiturates, benzodiazepines, cocaine, opiates, cannabinoids, phencyclidine, propoxyphene, and methadone at the screening and Day -1 tests.
13. Any methadone use 14 days prior to screening, and up to Study Day -1.
14. Has had a naltrexone implant in the past 24 months.

15. Has received treatment with an extended naltrexone product (e.g. Vivitrol) in the past 12 months.
16. Fails the naloxone challenge test (Appendix C)

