## **8.2 Day (-1) to day 3 (72 hr after dosing)**

Subjects will become in residence on day -1 and end this period of residency 72 hrs after implantation of BIOPIN 6 or placebo.

On day (-1), the following will occur: medical history update, Physical examination update, concomitant medication update, suicidality repeat, depression repeat, naloxone challenge repeat, , urine drugs repeat, pregnancy urine repeat. EKG repeat. Inclusion/exclusion criteria will be reverified.

On day 1 (0 hr—defined as the beginning of implantation), implantation of BIOPIN 6 or placebo will occur via [Appendix A](#). The measures used to prevent complications of implantation are given at the end of Appendix A.

**In addition to the implant parameters required by Appendix A**, the following assessments will be performed after implantation:

- distance (cm) to the incision of the closest palpable edge of the implant,
- photo of the implant site [outline each palpable implant with a blue marker on subject's skin, metric ruler in photo]

Between 0 hr and 72 hr, vital signs, adverse events, and clinical chemistries and hematology will be evaluated (per study timetable). Blood for PK will be taken Predose and at hours 1, 3, 6, 12, 24, 48 and 72. Acceptable time windows will be +/- 1 hr up to 24 hrs and +/-3 hrs for the 48 and 72 hr draws.

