### 5.2. Safety Endpoints

Safety endpoints will be analyzed over the entire treatment and follow-up period.

1. Adverse events (AEs) and serious adverse events (SAEs)
2. Vital signs
3. Physical examination of the nasal mucosa
4. Blood chemistries and hematology
5. Electrocardiogram (ECG) results
6. Suicidality: Frequency of subjects with suicidal ideation at any time during the treatment period using the Columbia-Suicide Severity Rating Scale (C-SSRS)
7. Depression: HAM-D17 Scores

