### **9.6.3 Vital Signs**

Vital signs will be presented as summary statistics and change from baseline. Values will be graded in accordance with the common criteria for adverse events (CTC-AE) version 5. The number and percentage of subjects with a vital sign measurements meeting grade 2 or greater criteria will be summarized by treatment group and CTC-AE grade. The percentage of ECG results considered abnormal and clinically significant will be presented as numbers and percentages for each timepoint. Vital signs and ECG results for all visits will be presented in the listings.

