**Table 30: Summary of ECG Results**

	Biopin 6 1 implant	Biopin 6 2 implants	Placebo 1 to 2 implants
Result	(N=xx)	(N=xx)	(N=xx)
Screening			
Normal	xx (xx.x%)	xx (xx.x%)	xx (xx.x%)
Abnormal, Not Clinically Significant	xx (xx.x%)	xx (xx.x%)	xx (xx.x%)
Abnormal, Clinically Significant	xx (xx.x%)	xx (xx.x%)	xx (xx.x%)
Other time points include Day -1, Weeks 4 and 8			
Normal	xx (xx.x%)	xx (xx.x%)	xx (xx.x%)
Abnormal, Not Clinically Significant	xx (xx.x%)	xx (xx.x%)	xx (xx.x%)
Abnormal, Clinically Significant	xx (xx.x%)	xx (xx.x%)	xx (xx.x%)

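### ECGs are summarised only as a three-way reader's call with no parameter named, so the planned tables are insensitive to a PR, QRS or QTc shift within normal limits; Table 30 also omits Week 12

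*Protocol*

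**What the plan says.** The Protocol Timetable (Section 2.2, repeated in SAP Section 4.2) schedules a 12-lead ECG at Screening, Day -1, Weeks 4 and 8, and Week 12 both before and after explant.

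- **Recording.** Protocol Section 8.1 says "A 12-lead resting EKG will be obtained". Section 8.2 has it repeated on Day -1: "EKG repeat. Inclusion/exclusion criteria will be reverified". No passage names an interval, a QT correction, replicates or a reader. The timetable footnotes, by contrast, itemise the vital signs, chemistry, hematology and coagulation tests.
- **Eligibility.** Exclusion criterion 1 relies on a judgement with no interval limit: "Clinically significant abnormal finding on the physical exam, medical history, electrocardiogram (EKG), or clinical laboratory results at screening".
- **Analysis.** Protocol Section 9.2 has no ECG analysis. SAP Section 5.2 names "Electrocardiogram (ECG) results" as a safety endpoint. SAP Section 9.6.3 plans this: "The percentage of ECG results considered abnormal and clinically significant will be presented as numbers and percentages for each timepoint". Table 30 has three rows per visit: normal, "Abnormal, Not Clinically Significant", and abnormal clinically significant. It covers Screening, Day -1 and Weeks 4 and 8.
- **Listings.** SAP Section 9.6.3 also promises a listing of ECG results for all visits. The listing shells (Section 13.2) are redacted.

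**The concern.** ECG intervals are continuous, but the plan condenses them into a reader's category. A drug effect that moves every subject by a similar amount, without taking anyone outside normal limits, need not change any category. Table 30 could then look the same with or without the effect.

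The plan treats comparable data differently and gives no reason. Vital signs, chemistry and hematology get values and change from baseline (Tables 25, 26 and 29) and figures (Figures 1 to 3). Pupil diameter in the naloxone challenge, a pre-dose eligibility test, is also summarised numerically. No ECG interval appears in any visible table or figure.

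This matters because the study is the first human use of this product, and Protocol Section 4.1 looks ahead to "BIOPIN 6 doses that lead to drug levels in excess of those resulting from Vivitrol administration". The ECGs at Weeks 4, 8 and 12 fall at visits with PK sampling, so numeric intervals could be read beside concentrations. The two Week 12 recordings allow a within-subject comparison around explant, which Table 30 as laid out would not show.

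**Working it through.** **No plan figure to reproduce.** The only design figure is 6 active subjects per dose level, called standard for PK studies (Protocol Section 9.4, SAP Section 8). No ECG calculation lies behind it. With 6:2 allocation and the two cohorts in the SAP, there are 12 active and 4 placebo subjects. Every millisecond figure below is an assumption and does not come from the documents.

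**1. Schedule against shell.** The timetable gives six ECGs per subject: Screening, Day -1, Week 4, Week 8, Week 12 pre-explant and Week 12 post-explant. Table 30 lists four. The two Week 12 recordings have no row, although SAP Section 9.6.3 promises a summary at each timepoint.

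**2. What a zero count says.** With no clinically significant ECG among n subjects, the exact two-sided 95% upper limit is 1 − 0.025^(1/n).
- n = 6: 1 − 0.025^(1/6) = 45.9%
- n = 12: 1 − 0.025^(1/12) = 26.5%

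**3. How often a within-range shift would surface as a category.** Assume baseline QTc with mean m of 400 or 410 ms and SD s of 15 or 20 ms, and a reader who calls an ECG abnormal when QTc exceeds 450 ms. For a uniform shift d, p = 1 − Φ((450 − m − d)/s), and the chance that at least 1 of 6 crosses is 1 − (1 − p)^6.
- d = 0: 0.3% (m = 400, s = 15) to 13% (m = 410, s = 20)
- d = 10 ms: 2% to 34%
- d = 20 ms: 13% to 65%

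For the 34% figure: (450 − 410 − 10)/20 = 1.5, so p = 0.0668 and 1 − 0.9332^6 = 0.34. Under these assumptions a 10 ms shift puts nobody over the limit in at least about two-thirds of six-subject groups.

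**4. What numeric change would give.** Assume an SD of QTc change from Day -1 of 10 to 15 ms. The 95% half-widths for the mean are:
- One dose, n = 6: 2.571/√6 = 1.05 SD, or 10.5 to 15.7 ms
- Both doses pooled, n = 12, no control: 2.201/√12 = 0.64 SD, or 6.4 to 9.5 ms
- 12 active versus 4 placebo: 2.145 × √(1/12 + 1/4) = 1.24 SD, or 12.4 to 18.6 ms
- One dose versus pooled placebo, 6 versus 4: 2.306 × √(1/6 + 1/4) = 1.49 SD, or 14.9 to 22.3 ms

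The limits in step 2 and the half-widths in step 4 describe different quantities, a proportion and a mean, and should not be read on one scale.

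**The case against.** A reader might infer that no interval values are recorded at all, and hence that the study cannot show a conduction or repolarisation shift. The documents do not support that. ECG results for all visits are to be listed, the listing shells are redacted, and the eCRF is not among the documents. Recording is unspecified, not excluded, and the conclusion reaches only the planned tables. Nor is heart rate without a numeric summary: sitting heart rate is in Table 29. Only the ECG-derived values lack one.

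A reader might also call Table 30 blind to a shift. It is not: it has three levels by visit, so movement from normal to abnormal not clinically significant would show. Step 3 supports insensitive, not blind.

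Three further objections carry weight:
- **Precision.** The 6.4 to 9.5 ms figure pools two doses and ignores placebo. Against the 4 placebo subjects the half-width roughly doubles, so a 10 ms shift would not be resolved. This stands, and limits the added summaries to description. The SAP tests no hypotheses anyway.
- **Risk premise.** Naltrexone has been approved in another form since 2010, and the adverse events in Protocol Section 4.4 include no ECG interval effect. The nonclinical section is redacted, so any cardiac reasoning there cannot be seen. This lowers the urgency but does not explain why ECG alone lacks numeric summaries.
- **Timing.** SAP Section 3 says the plan was finalised after dose-level 2 data were available. The change may therefore mean retrieving values from tracings whose retention is not documented.

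**Conclusion.** The point holds for the planned summaries. Neither document says which ECG parameters to record, and the only tabulation of a listed safety endpoint is a three-way call that would usually miss a uniform 10 ms QTc shift at n = 6 under the stated assumptions. The Week 12 omission from Table 30 is a plain mismatch with the timetable and needs no assumption.

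The gain from numeric summaries is real but modest: they would show direction and rough size by group and visit, with the half-widths in step 4 if the SD of change is 10 to 15 ms. They would not exclude a 10 ms effect against placebo. No ECG falls between Day -1 and Week 4, so an early effect would remain unseen however the recordings are summarised. This is an inexpensive improvement to the safety reporting and does not put the primary PK analysis in doubt.

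**What to change.** - **Protocol Section 8.1 and eCRF:** name ECG heart rate, PR, QRS, QT and QTcF as the values taken from each ECG already scheduled, using existing recordings where these have been obtained.
- **SAP Section 9.6.3 and Table 30:** add N, mean (SD), minimum to maximum, and change from Day -1, by group and visit. Include Week 12 pre-explant and post-explant as separate rows. Keep the three-way call beside them and extend it to Week 12.
- **Individual subjects:** add each subject's largest post-implant increase. With up to four post-implant recordings, the largest of several noisy changes tends to be positive even without a drug effect, so show it for placebo too.
- **Labelling:** state that these summaries are descriptive, and that pooled active change without placebo is uncontrolled.

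The cost is a few data fields and an extended table, with no extra ECG or visit. Machine-read intervals are noisy, so some spurious individual changes will need comment. If values were not captured at the time, someone must take them from stored tracings; if tracings were not kept, the report should say so.
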